Feasibility and Acceptability Data will be examined descriptively. Client Satisfaction Questionnaire score, rates of recruitment/retention, session attendance, and completion of between session goals will be compared to relevant previous trials. **Clinical outcome analyses** will focus on determining if BA-HD had clinically meaningful effects. For example, we will examine within participant effect size and response rates (using standard cut offs) on the PHQ-9. We will examine within participant change in our composite of behavioral risk factors in a similar manner. We will analyze data in an intent-to-treat manner.

Design Considerations

Choice not to use cardiac rehabilitation. Cardiac rehabilitation is the gold standard for targeting behavioral risk factors post-ACS and also improves depression symptoms. However, only a minority of ACS patients complete cardiac rehabilitation and those with depression are particularly unlikely to attend or complete.¹²³ Thus, if we conducted our treatment in a rehabilitation setting we would miss many of those with depression post-ACS. **Choice to enroll participants 2-12 months after ACS.** We considered enrollment of patients while in the hospital for ACS. We chose not to because: 1) there is a high rate of spontaneous recovery of hospital assessed

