We are recruiting ACS patients who are depressed and struggle with at least one behavioral risk factor post-ACS because this population will be the target of our intervention. We require patient willingness to change at least one risk factor because the treatment is designed for patients with some motivation to change. We limited enrollment to ages 18-75 because young children and geriatric patients may need tailored interventions. Fluency in English is required because (at this time) the BA-HD manual and forms are only in English and clinical supervisors are mono-lingual English speakers. Those with limited mental competency, a severe mental illness that would interfere with participation, or suicidality are excluded because these groups likely require different counseling strategies and/or a higher level of counseling care than provided by the proposed intervention. Our treatment manual was not designed for use in these populations. Those in hospice are excluded because the BA-HD manual does not address end of life issues. Those currently attending counseling for depression or health behavior change are excluded because these concurrent treatments would confound primary outcomes.

For **both Aims I and II**, we will enroll individuals of all racial and ethnic backgrounds. We plan to enroll ratios of minority groups that are consistent with the population of Minneapolis, MN. According to latest United States Census data, the racial composition of individuals living in Minneapolis, MN is 63.8% White, 18.6% Black or African American, 5.6% Asian, 2.0% American Indian/Alaska Native, 0.0% Native Hawaiian/Other Pacific Islander, and 4.4% two or more races. The ethnic composition of individuals living in Minneapolis MN is 10.5% Hispanic/Latino and 86.0% Non-Hispanic/Latino. Thus, we expect that 36.2% of the sample will be members of a racial minority group, and 10.5% of the sample will be of Hispanic/Latino ethnicity. We expect to enroll a sample that is 45% women which is representative of the gender distribution of ACS patients.^{1,45} Please see the Targeted/Planned Enrollment Table for a detailed distribution.

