Enrollment, Aim II: Participants will again be recruited through review of electronic medical records at Hennepin Healthcare. We will pull records of recent ACS hospital discharges that also have depression listed as a diagnosis. The Analytics Center of Excellence (ACE) team may identify names from EPIC to facilitate this. We will also review records of outpatient cardiology and ask outpatient cardiology providers to direct us to records of patients who might qualify. A research assistant will call patients to screen for eligibility using the above criteria. In addition, patients will be invited to call a research assistant themselves via use of a recruitment flyer will be provided to cardiology patients and providers (See attached). This flyer will be given to providers for distribution to interested patients and posted in clinic waiting rooms.

Those who qualify by phone screen will be invited to an in person meeting to provide informed consent
HSR#17-4351 [05.17.17][10.05.17][07.26.18][09.09.19][10.22.19][11.04.19][01.28.20]

and then complete a baseline assessment. The research assistant will then schedule the patient for a first session of BA-HD coaching at the Berman center or other Hennepin Healthcare facility (or in patient's home when needed).

Procedure, Aim II: Following informed consent, participants will complete self-report, interview, and anthropomorphic measures at enrollment and at end-of-treatment (i.e., following 12 weeks of BA-HD coaching). In addition, at end-of-treatment a 30 minute qualitative interview will be conducted. Qualitative questions will focus on the participants experience throughout the study (e.g., How was the screening process? How was the consent and enrollment process? What did you like and dislike about the coaching program?, etc). Data will also be pulled from the medical chart. Participants will be compensated \$30 per assessment and an extra \$20 for completion of the qualitative interview. Thus, participants completing could receive \$80 total for assessment completion. Transportation will also be provided or reimbursed as well.

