Minimization of risk from worsening of depression and emergent suicidality. **There is no evidence indicating that participation in this trial will worsen depression or cause suicidality.** However, given that post-ACS period can be a high stress time, it is likely that a minority of participants will experience worsening of depression during this study. A smaller minority may experience episodes of suicidality. Thus, we will monitor and respond to these issues in an ethically sensitive manner.

For aim II, we are only enrolling participants who are not currently in counseling for depression. Participants taking an anti-depressant medication at baseline and during the study will be allowed to participate. For ethical reasons, once enrolled we will not restrict anti-depressant medication treatment seeking in any way during the study (i.e., we will not ask participants to refrain from starting antidepressant medication during the study). We will carefully track antidepressant medication seeking outside of the study and will control for outside treatment in analyses as appropriate.

All participants will be assessed for depression using the PHQ-9 at all assessments. If a participant continues to report significant depression (i.e., PHQ-9 ≥ 10) at the end-of-treatment assessment, staff will 1) encourage the participant to discuss these symptoms with his or her medical providers and 2) provide a list of community psychiatric treatment referrals.

If a participant reports active suicidality (i.e., any recent suicidal attempts, suicidal gestures, or self-injurious behavior; any current plan or intent to engage in suicidal or self-injurious behavior) to any study staff at any time point, the participant will be assessed by [name] (a licensed clinical psychologist). [name] will assess the participant and respond in an appropriate and ethical manner according to the standards of care for suicide prevention (e.g., referral to immediate emergency psychiatric care if danger to self is imminent).

3. Potential Benefits of the Proposed Research

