Analytic plan
Healthy Heart Habits (H³)

NCT04158219

R03HL136540

3/8/22

Analytic plan.

Means, standard deviations, frequencies, and percentages will be calculated to describe the sample. Because the intent of the open pilot trial was feasibility and acceptability assessment to inform additional treatment refinement, analysis will emphasize descriptive characterizations of the data and calculation of effect sizes to examine clinical magnitude of preliminary effects. Descriptive data on baseline characteristics and treatment engagement will be presented on the entire sample, regardless of trial completion. Treatment satisfaction and pre- to post- change were calculated only for completers. No correction for multiple comparisons will be made. Analyses were performed in Stata SE 16.

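### Does the SAP need an analysis that controls for antidepressants started outside the study?

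*Protocol*

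**What the plan says.** Section 2b of the protocol, under worsening of depression and emergent suicidality, is permissive about drugs: "Participants taking an anti-depressant medication at baseline and during the study will be allowed to participate". New starts are not restricted, for ethical reasons. It continues: "We will carefully track antidepressant medication seeking outside of the study and will control for outside treatment in analyses as appropriate". The same section expects some deterioration: "it is likely that a minority of participants will experience worsening of depression during this study".

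The protocol's Analysis section does not mention outside treatment. It says the clinical outcome analyses "will focus on determining if BA-HD had clinically meaningful effects", and gives within-participant effect size and PHQ-9 response rates as examples.

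The SAP is a single paragraph. Because the pilot was meant to assess feasibility and acceptability, "analysis will emphasize descriptive characterizations of the data and calculation of effect sizes to examine clinical magnitude of preliminary effects". It adds: "Treatment satisfaction and pre- to post- change were calculated only for completers". It names no antidepressant variable, covariate, stratum or sensitivity display.

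**The concern.** Three things together look like a fault. The protocol undertakes to track a co-treatment and control for it. The SAP contains nothing that does so, and does not say the matter was considered and set aside. The protocol's Analysis section then words a one-arm, before-and-after change as though it could be credited to BA-HD.

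If several participants began an antidepressant between baseline and week 12, part of the PHQ-9 and CESD change would accompany that start, and a reader could not see how much. The direction is unknown: starters might improve more because of the drug, or they might be the people who were getting worse. An inflated or masked change could then mislead whoever decides whether to develop BA-HD further.

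**Working it through.** **Text.** The omission is real: nothing in the SAP takes up outside treatment. But the section 2b sentence leaves to judgement whether and how to control for it, so silence leaves the condition unresolved without contradicting it. On wording, the protocol's Approach section seeks only initial indications of efficacy, and Design Considerations defends an open trial over a randomised one because patient feedback is the main purpose. The SAP (3/8/22) is later than the last protocol date stamp (01.28.20) and uses the more cautious phrase about preliminary effects.

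**Inputs.** From the documents: N=20, one arm. Neither document gives a start rate, an SD, an expected change or a dropout rate, so there is no plan figure to reproduce. Assumed: k = 2, 4 or 6 starters; non-starters improve 3 PHQ-9 points; starters improve s = 6, 0 or -3 points (the last meaning they worsen by 3); SD of change 5.

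**Shift in mean change.** Shift = (k/20) × (s − 3).

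| k | s = 6 | s = 0 | s = -3 |
|---|---|---|---|
| 2 | +0.3 | -0.3 | -0.6 |
| 4 | +0.6 | -0.6 | -1.2 |
| 6 | +0.9 | -0.9 | -1.8 |

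At the extremes the pooled mean is 3 + 0.9 = 3.9 or 3 − 1.8 = 1.2. The sign depends wholly on who starts.

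**Sampling error.** The 95% half-width is t(0.975, n−1)/√n in SDs of change. At n=20 this is 2.093/√20 = 0.468, or 0.468 × 5 = 2.34 points. For the shift to equal it, starters would have to differ from non-starters by 2.34/(k/20): 23.4 points with 2 starters, 11.7 with 4, and 7.8 with 6. If only 16 complete (assumed) and 6 of them are starters who worsen by 3, the shift is (6/16) × (−6) = −2.25, against 0.533 × 5 = 2.67.

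**Likelihood of any starter.** 1 − (1 − p)^20 is 0.878 at p = 0.1 and 0.999 at p = 0.3. The situation would very probably arise; its effect on the estimate is what is modest.

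**What a with-and-without display would buy.** Dropping 2, 4 or 6 starters leaves 18, 16 or 14 people and half-widths of 0.497, 0.533 or 0.577 SD. The subset is chosen by something that happens after baseline. If starters are the people who are worsening, removing them makes the change look better. Natural recovery and regression to the mean remain in either figure, so neither is an effect of BA-HD.

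**The case for a change.** The strongest case for a change is that a conditional promise still has to be resolved somewhere, and the SAP is the natural place. A count of starts is itself descriptive, so it fits the SAP's stated emphasis. A baseline table could show existing use but not starts during the 12 weeks. Lying within sampling error is also no full defence: such a shift is systematic, and the magnitudes rest on chosen inputs. All of that stands, and it makes the counts worth reporting.

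Other supports are weaker. Section 1a says "these concurrent treatments would confound primary outcomes", but of counselling for depression or health behaviour change, current attendance at which is already an exclusion; it does not describe antidepressants that way. The protocol's background section reports that treating depression alone does not carry over to risk behaviours, so the behavioural composite is not an obvious casualty of antidepressant starts. The chart route, "Data will also be pulled from the medical chart", does not specify which data, and neither document says that counselling or rehabilitation begun during the study is recorded. Rewording the Analysis section would alter no result. Whether completers are the right set for pre-post change is a separate question.

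**Conclusion.** No change to the plan is needed. Followed as written, it yields a descriptive before-and-after change in completers, presented as preliminary, and that summary is sound as what it claims to be. The missing detail is one that analysts fill sensibly when reporting: how many participants were on an antidepressant at baseline, how many started or changed by week 12, and a sentence saying that no adjustment was made with 20 or fewer people.

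Under the assumed inputs the shift runs from +0.9 to -1.8 PHQ-9 points, against a half-width of 2.34. These are illustrations, not bounds, and they show neither an overstatement nor an understatement. The judgement rests mainly on the design: with one arm, no adjustment for co-treatment would turn the change into a BA-HD effect. It would be different in a controlled comparison, or if the SAP claimed efficacy from this change.

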Analytic plan
Healthy Heart Habits (H³)

NCT04158219

R03HL136540

3/8/22

Analytic plan.

Means, standard deviations, frequencies, and percentages will be calculated to describe the sample. Because the intent of the open pilot trial was feasibility and acceptability assessment to inform additional treatment refinement, analysis will emphasize descriptive characterizations of the data and calculation of effect sizes to examine clinical magnitude of preliminary effects. Descriptive data on baseline characteristics and treatment engagement will be presented on the entire sample, regardless of trial completion. Treatment satisfaction and pre- to post- change were calculated only for completers. No correction for multiple comparisons will be made. Analyses were performed in Stata SE 16.

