If at time of recruitment or any time during treatment/follow-up study staff determine that the participant does not have access to or has lost access to regular phone access, the participant may be offered use of a H³ provided cell phone. Participants who are issued a study phone will complete the H³ Study Issued Cell Phone Agreement form. Patient will be instructed to return the H³ provided phone to staff upon completion of the 12w outcomes visit or at any time if it is determined that the participant no longer qualifies for the study or is not adhering to the guidelines outlined in the H³ Study Issued Cell Phone Agreement. Upon return of the device, participants will qualify for a \$20 stipend.

See Appendix A: Study Issued Cell Phone Agreement.

References

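### The SAP limits pre- to post-treatment change to undefined completers, with no all-enrolled result, although the protocol commits the clinical outcomes to intent-to-treat

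*SAP*

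**What the plan says.** The protocol's Analysis section sets out the clinical outcomes. For depression, "we will examine within participant effect size and response rates (using standard cut offs) on the PHQ-9"; change in the behavioural composite is to be handled in a similar way. The paragraph ends: "We will analyze data in an intent-to-treat manner". No rule for missing data follows.

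The SAP (Analytic plan) uses two analysis sets. For the first, "Descriptive data on baseline characteristics and treatment engagement will be presented on the entire sample, regardless of trial completion". For the second, "Treatment satisfaction and pre- to post- change were calculated only for completers". It puts its emphasis on "calculation of effect sizes to examine clinical magnitude of preliminary effects". It contains no definition of a completer, no missing-data rule, no sensitivity analysis and no comment on the protocol's intent-to-treat sentence. It also states that "Analyses were performed in Stata SE 16", so the change results may already exist.

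**The concern.** The two documents assign different analysis sets to the same change outcomes, and the later one does not explain the switch. Because the preceding SAP sentence uses the whole sample, the restriction looks deliberate.

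The effect sizes are the SAP's efficacy summary, and the protocol's aim (Approach) includes early evidence of efficacy. A reader of those figures needs to know whom they describe and how far they depend on the people left out. The SAP supplies neither. Limiting satisfaction to those assessed is not a fault, because the protocol measures it only at end of treatment.

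**Working it through.** **1. Who is a completer?** Neither document says. Three meanings fit the text:

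- *Has an end-of-treatment assessment.* This is the most natural. The SAP contrasts completers with a sample taken regardless of trial completion, and satisfaction exists only at that visit. The protocol also attaches completion to assessments: "total for assessment completion" (Procedure, Aim II) and "upon completion of the 12w outcomes visit" (Amendment 2).
- *Attended at least 8 sessions*, the recommended minimum (protocol, BA-HD section).
- *Reached session 10*, which the protocol treats as the full course (Sessions 3-10).

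The first gives an observed-case analysis: poor attenders stay in, and unassessed participants leave. The other two would also discard 12-week data that exist, which is a larger departure from intent-to-treat.

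**2. Inputs.** The plan has no drop-out rate, SD or expected effect, so there is no figure of its own to reproduce. Only N = 20 (protocol, Approach) is documented. Assumed: m participants not assessed, completer mean change dc and leaver mean change dl, both in baseline SD units.

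**3. Mean change.** All-enrolled mean = [(20 − m)·dc + m·dl]/20, so completer minus all-enrolled = (m/20)(dc − dl). The difference is zero only if leavers change as much as completers.

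| m | dc = 0.5, dl = 0 | dc = 0.8, dl = 0 | dc = 1.1, dl = 0 | dc = 0.8, dl = 1.2 |
|---|---|---|---|---|
| 2 | 0.45 | 0.72 | 0.99 | 0.84 |
| 4 | 0.40 | 0.64 | 0.88 | 0.88 |
| 8 | 0.30 | 0.48 | 0.66 | 0.96 |

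Example: m = 4, dc = 0.8, dl = 0 gives 16 × 0.8/20 = 0.64.

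The standardiser matters. If the effect is divided by the SD of change (1 among completers) and leavers enter as zeros, the added zeros shrink that SD. For dc = 0.8, the m = 8 value is then 0.56 rather than 0.48.

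**4. PHQ-9 response.** With r responders among 20 − m completers, the all-enrolled rate lies between r/20 (missing counted as non-response) and (r + m)/20 (missing counted as response). For a 50% completer rate:

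| m | Completers | All enrolled |
|---|---|---|
| 2 | 9/18 | 45% to 55% |
| 4 | 8/16 | 40% to 60% |
| 8 | 6/12 | 30% to 70% |

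Each missing participant widens the range by 1/20, or 5 percentage points. The SAP does not mention response, so it is an inference that the completer restriction applies to it.

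**5. Attendance meaning.** Suppose 16 are assessed and k of them are excluded for low attendance, with completers at 0.80. The observed-case value is [0.80(16 − k) + k·dk]/16, where dk is the mean change of those excluded. For k = 2 (12.5% of the observed data) it is 0.70 if dk = 0 and 0.85 if dk = 1.2. For k = 4 (25%) it is 0.60 and 0.90.

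**The case against.** The strongest reply is that the conflict is softer than it looks. A single-arm trial has no randomised comparison to protect, so intent-to-treat can only mean keeping people in whatever their adherence. A paired change needs a second measurement, and the protocol names no imputation rule. If completers are simply those assessed at 12 weeks, the two sentences can coexist. That is a fair reading, but the SAP does not state it. An observed-case analysis still leaves out enrolled participants, and nothing is shown for them.

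Retention is a feasibility outcome and engagement is reported on everyone, so overall loss should be visible. That stands, but counts for each outcome and the effect of the loss on the estimates are not promised.

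The protocol also says that depression predicts drop-out and poor outcomes in lifestyle interventions, and that depressed patients are more likely to leave risk-factor programmes. This makes overstatement plausible. It does not settle the direction here: no drop-out data are given, and the sample is selected for depression throughout.

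Finally, the sizes are hypothetical and small beside sampling error. With m = 4, the exact 95% interval is 25% to 75% for 8/16 and 19% to 64% for 8/20. That also stands, and it limits how serious the point is.

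**Conclusion.** The point holds and should be fixed. The difference in wording, the missing definition and the missing sensitivity analysis are clear from the text.

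The size of any bias cannot be determined. Under the assumptions shown, a completer effect of 0.80 corresponds to an all-enrolled effect between 0.48 and 0.96 for 2 to 8 participants lost, depending on whether they were unchanged or improved by 0.4 more. The direction is open.

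The consequence is modest: the trial is descriptive, its main purpose is patient feedback on the manual (protocol, Design Considerations), and the SAP states the restriction openly. What is affected is how the preliminary effect sizes and response rates can be read.

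**What to change.** Reconcile the protocol's Analysis section with the SAP by replacing the SAP sentence with text such as:

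> Mean change from baseline includes every participant with a 12-week assessment, regardless of sessions attended. It is labelled observed-case and shown with n and the number missing for each outcome. Beside it, as a sensitivity analysis, is a result over all enrolled in which missing participants are assigned no change. PHQ-9 response is also given over all enrolled with missing counted as non-response, and tobacco abstinence over all baseline tobacco users with missing counted as use. Satisfaction is reported for those assessed at end of treatment.

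In addition:

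- State which SD standardises the effect sizes, because the no-change result depends on it.
- Label these rules as SAP choices, since the protocol names none.
- If the change results had already been calculated, as the SAP's past tense suggests, label the additions as made afterwards.
- If completers meant a session-attendance group, give the threshold.
- Disclose any completer-only result as a departure from the protocol.

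The cost is a wording change and a few lines of code on data already held. There is slightly more to report, and the figures may be less favourable.
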